RANDOMISED PLACEBO – CONTROLLED TRIAL OF DAILY ORAL VITAMIN D AND CALCIUM FOR THE SECONDARY PREVENTION OF OSTEOPOROSIS RELATED FRACTURES IN THE ELDERLY

Known as RECORD (Randomised Evaluation of Calcium OR vitamin D)

This protocol describes a major UK trial to establish or refute the claimed benefits of vitamin D and calcium, alone or in combination, to prevent bone fractures in the elderly. The trial is designed to be as simple as possible both for those participating and for those involved in clinical care. Research nurses will provide local co-ordination in all clinical centres.

1. THE REASONS FOR THE TRIAL

1.1 The burden of the problem

It is well known that osteoporotic fractures in the elderly create a significant and increasing burden of ill health. An estimated 50,000 to 80,000 women in the United Kingdom will suffer a hip fracture each year by 2006¹. The annual cost to the NHS is estimated at £258 million, and total public sector costs (including residential care) probably exceed £900 million².

1.2 The decision to test vitamin D and calcium

Of various putative strategies³⁻⁸ for preventing fractures, the most promising is supplementation with a combination of vitamin D and calcium.

In an exhaustive systematic review of previous trials of vitamin D and calcium for fracture prevention⁹, a total of 18 eligible randomised controlled trials were identified. (Most of the 42 studies excluded had no fracture outcome data.) Fifteen of the eighteen were explanatory type trials; each had less than 200 participants; most were conducted in institutional referral centres; and the principal outcomes were usually bone density or biochemical measurements. The three larger trials were pragmatic; they all had more than 500 participants, were community based, and focused on fractures. The results of these three trials appear contradictory.

The widely quoted French trial conducted by Chapuy and colleagues^{10,11} suggested that the combination of vitamin D and calcium significantly reduced the risk of fractures amongst elderly women in sheltered housing. In contrast, the large trial conducted in the Netherlands by Lips and colleagues¹², suggested no reduction in fracture risk from vitamin D alone. (This was despite an apparent improvement in bone density, raising questions about the validity of such measurements as a surrogate for fracture prevention.) The third larger trial¹³ suggested a benefit of calcitriol (a vitamin D analogue) in comparison with calcium. One of the studies excluded from this review is widely quoted as showing the effectiveness of a single dose of vitamin D in fracture prevention¹⁴. Quasi-random allocation to open vitamin D or no treatment was based on month of birth, and there is evidence of significant selection bias.

A more recently published trial¹⁵ amongst about 400 people provided further evidence that vitamin D and calcium taken together reduce the risk of fracture. Current evidence therefore suggests that it is this combination, which is most likely to be effective. However, because of the relatively high cost of calcium, this is unlikely to be cost saving, especially for primary prevention (unless the price falls significantly). Vitamin D alone, on the other hand, is more attractive because of its low cost but evidence of its effectiveness is much less promising.

1.3 The questions which this protocol will address

The trial described in this protocol is therefore needed urgently because (a) the importance of calcium, alone or in combination with Vitamin D, must be clarified; (b) vitamin D alone should still be tested because if effective it could be very cost effective; (c) without this trial vitamin D and calcium use is likely to increase with major resource implications and (although very unlikely) possible hazards.

1.4 The advantages of a secondary prevention trial

The trial will be of secondary prevention in the setting of current NHS provision of fracture care. This has advantages. First, those who have sustained a fracture constitute a high-risk group for further fracture: 5-10 fold for another hip fracture after a first hip fracture, and about two-fold after other types of fracture^{16,17}.

Secondly, virtually all patients with new fractures are in contact with the health services, and this offers an efficient method of identification both for a trial, and for prevention should this trial demonstrate effectiveness. Thirdly, during a trial, provided that minimal demands are made on clinic staff, research staff may efficiently recruit participants. Fourthly, after a recent fracture, older people may be particularly receptive to prophylactic options.

2. TRIAL RECRUITMENT

2.1 Who will be considered for trial entry?

The trial will involve people aged 70 or over who have had a previous fracture:

- (i) Those who have sustained a fracture (except cervical spine, skull or face) in a fall from no more than a standing height within the previous two years (while eligible patients may have sustained more than one fracture, those who have high energy transfer injury will not be eligible)
- (ii) Those with a clinical vertebral fracture (defined as a definite clinical event with radiological evidence* of an incident vertebral fracture)

Potential participants will be identified by study nurses based in each clinical centre from amongst patients attending hospital as outpatients or inpatients. A log will be kept of patients meeting these criteria, describing the reasons if they are not subsequently recruited to the trial. (Depending on the numbers of people attending hospital who are recruited, additional patients may also be identified from medical records as having sustained an eligible fracture in the preceding two years.)

2.2 Informing potential participants about the trial

The nurse will describe the study to potentially eligible people backing oral information with the standard study information leaflet (Appendix 1). Those approached may choose to involve an accompanying person.

^{*} lateral x-ray shows at least a 20% reduction in anterior, middle or posterior height of any vertebra and a 10% reduction of the projected vertebral area

2.3 Ruling out uncommon reasons for exclusion

Amongst those who indicate that they are likely to participate, the nurse, using a combination of questions and casenote review, will then check that none of the following exclusion criteria apply:

- Bed or chair bound prior to index fracture
- Unlikely to be able to comply with the protocol (e.g. abbreviated mental test score¹⁸ of six or lower)
- Suffering from a cancer likely to metastasise to bone (e.g. breast, kidney, lung, thyroid, and prostate)
- Fracture associated with pre-existing local bone abnormality
- Known hypercalcaemia or active renal stone disease (documented in last 10 years)
- Current daily treatment with >200 IU vitamin D or >500mg calcium; had fluoride, bisphosphonates, calcitonin, tibolone hormone replacement therapy, selective estrogen receptor modulators or any vitamin D metabolite (such as calcitriol), in the last 5 years; vitamin D by injection in last year
- Unlikely to complete the study (e.g. known to be leaving the UK to reside abroad, or life expectancy less than six months)

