2.6 Instructions about what is involved

The nurse will then give a standardised description of participation. This will include an information sheet about precautions against falls and exercise as possible means of fracture prevention (Appendix 4). The nurse will explain the arrangements for supplying the tablets (see below), and how they should be taken. The hospital case notes will be labelled at this time with a request to send to the local clinical coordinator copies of discharge summaries and letters if the patient has any further contact with the hospital.

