4.2 Checking that all is well

Two weeks after recruitment and thereafter when judged necessary, the enrolling nurse will contact the participant to check the place of residence, and that there have been no problems taking the tablets.

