4.3 Four monthly postal contact

Each fresh supply of materials will contain a brief form for completion by the participant (Appendix 8). This has the following purposes:

- i) confirmation that the materials arrived safely
- ii) collection of information about the preceding four months: any new fracture; any admission to hospital; and any change in residence
- iii) details of tablet compliance from the preceding week: whether the tablets have been taken, how often, and reason for stopping if applicable.

As a further measure of compliance, a five percent randomly selected subsample of recruits will be asked to return all unused supplies for a tablet count. A detailed protocol is provided in Appendix 9.

4.4 Additional information sought by post at four, twelve, twenty-four, thirtysix and forty-eight months after entry

Longer forms will be sent at four, twelve, twenty-four, thirty-six and forty-eight months (Appendix 10) which, in addition to the above, will collect the following information:

- i) falls in last week
- ii) the EQ-5 questionnaire
- iii) the SF-12 questionnaire
- iv) Diabetic or not, use of oral hypoglycaemics and/or insulin

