4.5 Notifications by general practitioners

Stickers and the information sheet will ask the general practitioner to notify the Trial Office by phone if the participant:

- (i) sustains a new fracture
- (ii) moves to another practice

- (iii) has a suspected adverse event related to the trial, specifically developing renal insufficiency (creatinine greater than 250 micromols per l), renal stones, or hypercalcaemia (based on local reference standards)
- (iv) develops diabetes mellitus requiring oral hypoglycaemics and/or insulin.
- (v) dies (and cause of death)

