The incidence of adverse effects from the proposed dosage of vitamin D and calcium is anticipated to be very low - in the systematic review renal insufficiency or stones were reported for 4/4025 (0.1%) and gastro-intestinal disturbances for 93/3892 (2.4%).

Collaborators and participants may write to the chairman of the steering committee about any worries they may have about the trial. If concerns arise about particular side-effects or about particular types of participants, these will be relayed to the Chairman of the Data Monitoring Committee.

If clinically indicated, rapid unblinding of trial materials will be available through the trial office.

The Multicentre Research Ethics Committee for Scotland has approved the trial. The trial will be conducted according to the MRC Good Clinical Practice Guidelines (1998)²².

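### Section 2.3 excludes known hypercalcaemia and active renal stones but not known renal insufficiency, although section 4.5(iii) names all three as suspected trial-related harms

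*Protocol*

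**What the plan says.** **Entry.** Section 2.3 has seven exclusion bullets, checked by the nurse "using a combination of questions and casenote review". The one concerned with calcium and the kidney reads "Known hypercalcaemia or active renal stone disease (documented in last 10 years"). The only other kidney wording is kidney cancer, listed as a tumour that may spread to bone. Another bullet covers recent bone-active drugs, including "any vitamin D metabolite (such as calcitriol), in the last 5 years", and current calcium above 500 mg daily.

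**Entry data.** The items listed in section 2.5 include diabetes, thiazides, thyroxine and prednisolone. They include no renal history and no creatinine.

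**Harms.** Section 4.5(iii) asks the general practitioner to report a suspected trial-related adverse event, "specifically developing renal insufficiency (creatinine greater than 250 micromols per l), renal stones, or hypercalcaemia (based on local reference standards"). Section 8.3 gives the background rate from the systematic review: "renal insufficiency or stones were reported for 4/4025 (0.1"%).

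**Follow-up.** No creatinine or calcium measurement is scheduled in the protocol text. News of a renal problem would come through general routes:
- hospital notes carrying "a request to send to the local clinical coordinator copies of discharge summaries and letters" (2.6)
- a nurse contact at two weeks to check, among other things, "that there have been no problems taking the tablets" (4.2)
- four-monthly forms on "any new fracture; any admission to hospital; and any change in residence" (4.3), plus tablet compliance and reasons for stopping
- the general practitioner (4.5), the best contact (4.6) and the clinical co-ordinator (8.1)
- data monitoring committee review (8.3)

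**The concern.** The protocol treats three conditions as possible harms of the supplements. It screens out known cases of two and gives no reason for leaving out the third.

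The remaining bullets (vitamin D metabolites, calcium above 500 mg, doubtful compliance, short life expectancy) remove some people with renal insufficiency. They do not remove a mobile, mentally able patient aged 70 or over with a recorded creatinine above 250 micromol/l who takes none of the listed drugs.

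Two things are at stake. The first is exposure: such a person could be allocated up to 1 g calcium and 800 IU vitamin D3 daily, with a median follow-up of three years. The second is the reading of the safety data. Section 4.5(iii) asks about *developing* renal insufficiency above 250. Someone already above 250 has no threshold left to cross, and no item listed at entry would show that the condition was there beforehand.

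**Working it through.** **Step 1. Section 4.5(iii) against section 2.3**

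| Event named in 4.5(iii) | Known cases excluded in 2.3? |
|---|---|
| Renal insufficiency (creatinine above 250) | No |
| Renal stones | Yes, if active and documented in the last 10 years |
| Hypercalcaemia | Yes, if known |

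**Step 2. The protocol's own figure.** 4/4025 = 0.099%, which reproduces the stated 0.1% (exact 95% interval 0.03% to 0.25%). This pools insufficiency with stones. Applied to the whole trial, 6,500 × 4/4025 = 6.5, so about six such events would be expected. Even a handful of existing cases reported as new would blur a count that small.

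**Step 3. How many people.** The document gives no prevalence. Purely as an illustration, assume that 0.2%, 0.5% or 1% of entrants have recorded creatinine above 250 after all other exclusions. With four equal groups (also assumed), three of the four carry an active supplement:
- 6,500 × 0.002 = 13; × 3/4 = 9.8
- 6,500 × 0.005 = 32.5; × 3/4 = 24.4
- 6,500 × 0.01 = 65; × 3/4 = 48.8

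**Step 4. Room in the sample size.** Section 7.1 wants 4,000 in the analysis, recruits 6,500 and expects 35% losses. 4,000/0.65 = 6,154, and 6,500 − 6,154 = 346, or 5.3% of 6,500. The pooled-variance formula for 15% versus 12% gives 2,036 per group, 4,072 in total, for 80% power; at exactly 4,000 the power is 79.3%. On that stricter count, 4,072/0.65 = 6,265, which leaves 235, or 3.6%.

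**Step 5. Power after the exclusion.** With *n* per group and a two-sided 5% test,

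power = Φ{[0.03√n − 1.96√(2 × 0.135 × 0.865)] / √(0.15 × 0.85 + 0.12 × 0.88)} = Φ{(0.03√n − 0.9472)/0.4828}.

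Analysable numbers are 0.65 × entrants, split into equal halves, with nobody replaced:

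| Excluded (assumed) | Analysable | Power |
|---|---|---|
| None | 4,225 | 81.4% |
| 0.2% | 4,217 | 81.4% |
| 0.5% | 4,204 | 81.2% |
| 1% | 4,183 | 81.1% |

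For the first row, 0.03 × √2,112.5 = 1.3789, and (1.3789 − 0.9472)/0.4828 = 0.894, so Φ = 0.814.

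**The case against.** The strongest reply is that notification and exclusion are different functions. Section 4.5(iii) concerns incident events, and nothing says that each must also bar entry: new diabetes is notifiable yet diabetics are admitted, and gastrointestinal symptoms are a listed adverse effect with no matching exclusion. This stands to the extent that sections 2.3 and 4.5 do not contradict each other. The parallels are weak, though. Diabetes is listed apart from the suspected adverse events, and gastrointestinal symptoms are not an organ-safety condition of the same kind.

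A reader might infer that people with existing renal insufficiency would be harmed. The document does not say so. Its only rate concerns events during earlier trials, and it expects adverse effects to be very uncommon. The point rests on the protocol's own list of suspected harms, not on a demonstrated risk.

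A reader might also infer that deterioration would go unseen. That is too strong. Besides the reporting routes above, the general practitioner is told of participation (4.1), rapid unblinding is available (3.4, 8.3), the co-ordinator carries local clinical responsibility (8.1), and an ethics committee has approved the trial. What is absent is scheduled measurement. The entry form, leaflet and practice letter are not available here and may mention renal disease, but a form item would not be an exclusion.

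Finally, a simple trial needs a short exclusion list, and 250 is a reporting threshold reused for eligibility. Both remarks are fair. The added phrase lengthens one bullet only, and 250 is the only creatinine value that the protocol defines.

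**Conclusion.** The gap is real and minor. Known renal insufficiency is the only one of the three harms named in section 4.5(iii) whose known cases may enter, and nothing in the protocol explains why. Eligibility is fixed in the protocol, so an unseen analysis plan would not supply the exclusion.

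The number affected is unknown and probably small; the figures of 13 to 65 people rest wholly on the assumed 0.2% to 1%. It does not follow that the fracture comparison is biased. The same rule applies to every arm before randomisation, so existing cases add noise to the renal safety count but no systematic difference between groups. Nor would one phrase close the gap, because it can act only on what is recorded.

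This is a cheap improvement that the sponsor could make, held with medium confidence.

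**What to change.** In the section 2.3 bullet, insert after known hypercalcaemia: *known established renal insufficiency (documented creatinine greater than 250 micromol/l, not attributed to a temporary perioperative rise)*. Leave the stone-disease wording as it stands. The check belongs in the casenote review that the nurse already does, with no blood test and no new form. If the sponsor prefers to admit these patients, a sentence giving the reason would serve instead.

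The words on established disease and perioperative rises matter. Section 2.4 allows hip-fracture inpatients to be approached soon after the second post-operative day, when a single recent value may mislead. The nurse may sometimes need the co-ordinator's judgement on whether a recorded value, perhaps an old one, reflects established disease.

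The cost is a few lost recruits, well within the room shown above on the assumed range, and slightly narrower generalisability. Unrecorded renal insufficiency and values below 250 would still enter, just as unrecognised hypercalcaemia does now.

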2.4 Consent to participate

Once eligibility has been confirmed, the nurse will ask if the potential participant is ready to decide whether or not to join the trial. If so, she will give the participant a consent form (Appendix 2). (If not, she will arrange to make contact again about a week later.) After she has checked that the consent form is understood, the nurse will invite the participant to sign the form, add her own name and countersign it. (Consent will only be sought from in-patients with hip fractures after the second post-operative day at the earliest.) One copy of the consent form will be given to the participant, another will be filed in the hospital case notes, and the third will be posted to the Trial Office.

2.6 Instructions about what is involved

The nurse will then give a standardised description of participation. This will include an information sheet about precautions against falls and exercise as possible means of fracture prevention (Appendix 4). The nurse will explain the arrangements for supplying the tablets (see below), and how they should be taken. The hospital case notes will be labelled at this time with a request to send to the local clinical coordinator copies of discharge summaries and letters if the patient has any further contact with the hospital.

3. TRIAL INTERVENTIONS

3.1 Two tablets taken each day

Participants will be asked to take two tablets every day with or after food.

Those allocated vitamin D will have a daily supplement of 800 IU (D₃).

Those allocated calcium will have a daily supplement equivalent to 1g elemental calcium.

Those allocated vitamin D and calcium in combination will have a daily supplement of 800 IU (D_3) and 1g elemental calcium.

3.2 The trial's 'factorial'design

The trial will use a 2 by 2 factorial design to test not only whether vitamin D and calcium on their own are effective, but also whether there is extra effectiveness from the combination. For this reason allocation will be to one of four groups:

| | Calcium supplement (1g daily) | No calcium supplement |
|---|---|-----------------------|
| Vitamin D supplement (800 IU D₃ daily) | (a) Combined vitamin D and Calcium tablets | (b) Vitamin D tablets |
| No vitamin D supplement | (c) Calcium tablets | (d) Placebo tablets |

3.3 Treatment allocation

The trial allocation will be computer-generated in the Trial Office. After stratification by trial centre, balance in respect of other key prognostic variables – age (under 80 or 80 and over), sex, time since fracture (previous three months or longer) and type of enrolling fracture (proximal femur, distal forearm, clinical vertebral and other) – will be ensured by a process of minimisation.

3.4 Tablet supplies and delivery

The allocated trial tablets will be supplied in screw top containers labelled with the participant's name, date of supply and batch number, with a unique study number, allowing rapid unblinding if later deemed necessary. Tablets sufficient for four months will be packaged together for dispatch to individual participants.

In general, supplies will be posted directly to the participant from the Trial Office. There will, however, be flexibility in the way used to get the initial supply to a participant. At the time of trial entry the study nurse will be able to choose whether the materials are posted or given to a participant directly, and if posted where they should be sent to. Where there are compelling reasons for giving the first supply directly to the participant (for example, because of current in-patient care), the nurse will be sent the materials from the Trial Office and s/he will then pass them on to the participants.

Thereafter, supplies will be posted directly to all participants at four monthly intervals using standardised packaging.

4. SUBSEQUENT ARRANGEMENTS

4.1 Informing key people

Following formal trial entry, the Trial Office will also contact:

- i) the *general practitioner* letting the practice know about participation in the trial and the (few) implications for the practice. This letter (Appendix 5) includes a brief description of the trial together with a request that the general practitioner notifies the Trial Office if any prespecified events, such as the patient dying, occur (see section 4.5 below)
- ii) the 'best contact' asking for assistance if circumstances change (see below) (Appendix 6)
- iii) the *local study nurse* to confirm that the participant has been recruited, giving the study number and date of despatch of materials (Appendix 7)

4.2 Checking that all is well

Two weeks after recruitment and thereafter when judged necessary, the enrolling nurse will contact the participant to check the place of residence, and that there have been no problems taking the tablets.

